| 11.4. Prior to Study Initiation | 19 |
| 11.5. Site Initiation Visit (SIV) | 19 |
| 11.6. Interim Monitoring Visits (IMVs) | 20 |
| 11.7. Sponsor Audits and Regulatory Inspection | 20 |
| 11.8. Close Out Visit (COV) | 20 |
| 11.9. Documentation of Site Visits | 20 |
| 11.10. Data Handling and Record Keeping Requirements | 20 |
| 11.11. Data Recording and Record Retention | 20 |
| 12. DEVIATIONS FROM PROTOCOL | 21 |
| 12.1. Protocol Deviation Reporting Requirements | 21 |
| 13. PUBLICATION POLICY | 21 |
| 13.1. Multicenter Publication | 21 |
| 13.2. Investigator Publication | 21 |
| 13.3. Authorship | 22 |
| BIBLIOGRAPHY | 23 |

ABBREVIATIONS & DEFINITIONS

| | |
|------------------|---|
| AE | Adverse Event |
| ADE | Adverse Device Effect |
| AP | Anterior-posterior |
| ASIS | Anterior Superior Iliac Spine |
| CAPA | Corrective and Preventive Action |
| CCD angle | Caput-collum-diaphyseal angle |
| COV | Close Out Visit |
| CRF | Case Report Form |
| EC | Ethics Committee |
| FDA | Food and Drug Administration |
| GCP | Good Clinical Practice |
| ICF | Informed Consent Form |
| ICH | International Conference on Harmonisation |
| IFU | Instructions for Use |
| IMV | Interim Monitoring Visit |
| PI | Principal Investigator |
| SAE | Serious Adverse Event |
| SADE | Serious Adverse Device Effect |
| SIV | Site Initiation Visit |
| SQV | Site Qualification Visit |
| THA | Total Hip Arthroplasty |
| USADE | Unanticipated Serious Adverse Device Effect |

PROTOCOL SYNOPSIS

| | |
|----------------------|---|
| Title of Study: | Intraoperative case series study: trial rasp position versus SL-PLUS® MIA Ti/HA femoral hip stem position |
| Study Type: | Post-market, Evidence collection |
| Study Device: | SL-PLUS® MIA Ti/HA femoral hip stem |
| Indications: | 
 Advanced hip joint wear due to degenerative, post-traumatic or rheumatoid arthritis Fracture or avascular necrosis of the femoral head Follow-on conditions after previous surgery such as osteosynthesis, joint reconstruction, arthrodesis, hemiarthroplasty or total hip replacement. |
| Study design: | Observational, single arm, prospective, multi-center, case series study |
| Study Objective: | The study objective is to evaluate if there is a difference between the position of the last trial rasp and the final implant position of the SL-PLUS® MIA Ti/HA femoral hip stem. |
| Primary Endpoint: | Mean difference between the position of the last trial rasp and the final implant position as measured by an intraoperative fluoroscopic measurement |
| Secondary Endpoints: | Discrepancy of leg length after total hip arthroplasty Intraoperative complications |
| Length of Study: | 3 months enrollment period = total study duration |
| Number of Sites: | up to 4 sites |
| Sample Size: | 40 |
| Inclusion Criteria: | 
Subject:
 
 requires primary THA with the SL-PLUS® MIA Ti/HA femoral hip stem is at least 21 years of age at the time of surgery is skeletally mature in the PI's judgement has consented to participate in the study by signing the Ethics Committee (EC) approved Informed Consent Form (ICF) |
| Exclusion Criteria: | 
Subject:
 
 requires the use of a ceramic-on-ceramic bearing has infections, acute or chronic, local or systemic has severe muscle, nerve or vascular diseases that endanger the respective limb has lack of bone substance or defective bone quality that jeopardizes the stable seating of the prosthesis has any concomitant disease that may jeopardize implant function has a known allergy to study device or one or more of its components requires a revision surgery and has extensive bone defects has diagnosis of an immunosuppressive disorder is pregnant |

1. BACKGROUND AND STUDY RATIONALE

As the incidence of joint disease continues to increase, an ever growing percentage of the affected population will undergo total hip arthroplasty (THA). With increasing life expectancy the demand on these hip arthroplasties is rising [1].

The success of the hip implant is directly linked to the correct position of the femoral stem. A malposition of the femoral stem may cause leg length differences, tension problems, increased risk of luxation, increased risk of impingement and increased wear which may be followed by early loosening.

Konyves et al. examined leg length inequality in 90 patients after THA. 62% of patients were observed having a leg length discrepancy after THA being associated with back pain, gait disorders and following general patient dissatisfaction. The authors further showed that in 98% of patients with leg length discrepancy, the discrepancy occurred in the femoral component strengthening the importance of appropriate placement of the femoral component [2].

The correct position of an uncemented hip stem is planned preoperatively. During surgery, the final position of the rasp should correspond to the preoperatively determined position and the same position should be adopted by the uncemented femoral stem [3].

Barink et al. examined this rasp-stem correspondence for two different rasp-stem systems in a laboratory study. They observed an average rasp-stem mis-match in three orthogonal directions smaller than 2mm for both the CLS system (Centerpulse/Zimmer Warsaw, IN, USA) and the CBC-T system (Mathys, Bettlach, CH). Based on good long term results documented for the CLS system, the authors considered the measured difference as being of very low clinical relevance [3].

In contrast, Hozack et al. showed that malpositioning of the stem is not a rare event in real life surgeries. Hozack et al. showed by observation of 100 uncemented THA with the modular Taperloc prosthesis (Biomet, Warsaw, IN, USA) that the preoperatively planned stem position could not be achieved for all cases. In 19 cases the neck length needed to be adapted after insertion of the femoral stem to achieve stability or avoid a leg length difference [4].

As indicated by Hozack et al., femoral malposition can be corrected to some degree by the selection of the appropriate components when using a modular hip system. Possibilities for correction of femoral malposition are more limited when using a mono-block system. Although small differences in the position between the final rasp and the stem are not of clinical significance, femoral malpositioning should be avoided to the highest degree possible as it forms a potential source of clinical complications [3].

The SL-PLUS® MIA Ti/HA femoral hip stem is a dual-tapered straight stem with a rectangular cross section. The SL-PLUS® MIA Ti/HA stem belongs to the SL-PLUS® family and is based on the SL-PLUS® standard stem.

The Ti/HA coating causes an oversize of 0.7mm compared to the size of the rasp which might prevent the implant from being inserted as deeply as the rasp [5].

The purpose of this study is to evaluate if there is a difference between the final position of the femoral stem and the last trial rasp when using the SL-PLUS® MIA Ti/HA femoral hip stem with the appropriate set of instruments. In case a difference is detected this study also serves to quantify the difference in rasp and stem position for the SL-PLUS® MIA Ti/HA femoral hip stem.

2. STUDY OBJECTIVES

The study objective is to evaluate if there is a difference between the femoral position of the last trial rasp and the final implant position of the SL-PLUS® MIA Ti/HA femoral hip stem.

2.1. Primary Endpoint

The primary endpoint is the mean difference D between the position of the last trial rasp and the final implant position of the SL-PLUS® MIA Ti/HA femoral hip stem. The difference D is determined by analyzing standardized fluoroscopic images taken during surgery.

The difference D is given in mm and is defined as $D = x_1 - x_2$ with x_1 being the distance between the shoulder of the trial rasp and the tip of the greater trochanter and x_2 being the distance between the shoulder of the implant and the tip of the greater trochanter.

The distance to be measured is shown in Figure 1: Example of pre-operative planning.

Figure 1 Pre-operative planning: x = distance between shoulder of implant and the tip of the greater trochanter [mm]

The diameter of the trial head and the final ball head will be measured to calibrate the size of the digital image.

The study hypothesis is defined as:

H_0 : The null hypothesis is that there is no mean difference between the position of the last trial rasp and the final implant position of the SL-PLUS® MIA Ti/AH femoral hip stem.

H_1 : The alternative hypothesis is that there is a mean difference between the position of the last trial rasp and the final implant position of the SL-PLUS® MIA Ti/AH femoral hip stem.

2.2. Secondary Endpoints

The secondary endpoints include a measurement of leg length discrepancy preoperatively and after insertion of the SL-PLUS® MIA Ti/HA femoral hip stem. In addition, intraoperative complications will be collected.

3. STUDY DESIGN

This is an observational, single arm, prospective, multi-center, case series study to collect intraoperative data from 40 subjects implanted with the SL-PLUS® MIA Ti/HA femoral hip stem at 4 sites in Europe.

Data from eligible subjects, who have provided written and informed consent for the collection of their coded data, will be recorded on specially designed case report forms (CRFs).

No follow-up visits after surgery are planned for study participants. Therefore, total study duration for study participants is completed with surgery.

A final data analysis describing the study outcome is planned after completion of study assessments.

4. STUDY DEVICE

The SL-PLUS® MIA Ti/HA femoral hip stem is a dual-tapered straight stem with a rectangular cross section. The SL-PLUS® MIA Ti/HA stem belongs to the SL-PLUS® family and is based on the anchorage principles of the SL-PLUS® stem.

The SL-PLUS® MIA Ti/HA stem has a minimal invasive surgery-friendly design allowing the rasps and the stem to be introduced into the bone in a curved manner. This allows reduction of bone resection in the trochanteric region, minimizes the risk of fracture, maximizes preservation of the tendon insertions and protects muscles and skin.

The SL-PLUS® MIA Ti/HA stem has a Ti/HA multi layer coating in the proximal area of the stem leading to accelerated and increased bone on-/in- growth with the aim of avoiding development of radiolucent lines by enhancement of load transmission in the metaphyseal region.

The SL-PLUS® MIA Ti/HA stem is made from Ti6Al7Nb Titanium Aluminium Niobium alloy. Two offset options are available. The standard stem is available with a Caput-collum-diaphyseal angle (CCD) of 131° and the lateral stem is available with a CCD angle of 123°.

The standard stem is available in 128mm to 188mm length. The lateral stem is available in 136mm to 188mm length.

4.1. Surgical Technique

All study related procedures with the SL-PLUS® MIA Ti/HA femoral hip stem must be performed according to the recommended surgical technique described in the labeling and in the instructions for use (IFU).

Surgeons selected to participate in this study will be familiar with implanting SL-PLUS® MIA Ti/HA femoral hip stem and have evidence of training and expertise in the study procedure.

4.2. Device Accountability

Device accountability is not required to be recorded as sites will be expected to use products from their own stock. Device information will be recorded on the CRF and chart sticks will be kept within the CRF to document the devices used.

5. STUDY POPULATION

5.1. Subject Screening & Enrollment

To eliminate the potential for selection bias, Investigators should consecutively pre-screen all subjects undergoing THA with the SL-PLUS® MIA Ti/HA femoral hip stem. In order to do so, only the existing information obtained per standard routine medical procedures will be used. No study-specific screening procedures, activities or questionnaires will be performed during pre-screening.

Once a subject has completed the informed consent procedure and signed the Informed Consent Form (ICF), the Principal Investigator (PI) or delegated study research staff can complete the screening process with the subject. All potential subjects who undergo the screening process will be documented on a Screening and Enrollment Log, on which reasons for exclusion from or denial to participate should be noted.

5.2. Subject Inclusion Criteria

Subject:

- requires primary THA with the SL-PLUS® MIA Ti/HA femoral hip stem
- is at least 21 years of age at the time of surgery
- is skeletally mature in the PI's judgment
- has consented to participate in the study by signing the EC approved ICF

5.3. Subject Exclusion Criteria

Subject:

- requires the use of a ceramic-on-ceramic bearing
- has infections, acute or chronic, local or systemic
- has severe muscle, nerve or vascular diseases that endanger the respective limb
- has lack of bone substance or defective bone quality that jeopardizes the stable seating of the prosthesis
- has any concomitant disease that may jeopardize implant function
- has a known allergy to study device or one or more of its components
- requires a revision surgery and has extensive bone defects
- has diagnosis of an immunosuppressive disorder
- is pregnant

6. STUDY PROCEDURES

6.1. Study Schematic

The study duration for each subject is defined as the time between signing the ICF and time of completion of surgery (transfer to general ward). The intervals and schedule of events are provided in Table 1.

Table 1 Schedule of events

| Schedule of events | Pre-Operative | Surgery / Peri-Operative |
|--|---------------|-----------------------------|
| Patient Information and Informed Consent | ✓ | |
| Inclusion/Exclusion Criteria | ✓ | |
| Demographics/Medical History | ✓ | |
| Radiographic assessment | ✓ | |
| Operative Data Collection | | ✓ |
| Fluoroscopic assessment | | ✓ |
| Measurement of leg length discrepancy | ✓ | ✓ |
| Adverse Event Assessment | ✓* | ✓ |
| End of Study/Exit | | ✓ |

*if applicable

The following algorithm should guide through the steps of pre-screening, screening, enrollment and study conduct in accordance with sections 6 Study Procedures and 7 Subject Completion and Disposition of this protocol.

[figure not shown]

Figure 2 Overview of pre-screening, screening, enrollment and study conduct

6.1.1. Assessment 1: Pre-Operative Visit

During the pre-operative visit a standard anterior-posterior (AP) pelvic hip radiograph will be taken.

The AP view should include full pelvic overview. The pre-operative radiograph will be taken for diagnostic purposes and THA planning. The Investigator will analyze the pre-operative radiograph and collect the following information on the appropriate CRF:

- diagnosis for THA
- bone quality according to Dorr et al. [6]
- distance x_1 between the shoulder of the implant and the tip of the greater trochanter, reference Figure 1, measured during preoperative planning

Based on the pre-operative planning, implant sizes planned to be used during THA will be recorded on the CRF. The leg length difference will be measured by the Investigator or designee during the preoperative physical examination. The length of each lower extremity is determined in cm by measuring the distance between the anterior superior iliac spine (ASIS) and the medial malleolus by using a measuring tape with the subject in supine position [7]. Measured distances will be recorded on the appropriate CRF.

6.1.2. Assessment 2: Surgery

During surgery two fluoroscopic AP images will be taken showing the position of the final trial rasp with trial head and the final position of the implanted stem with final ball head. The joint will be reduced at the time the images are taken. The AP view should include the full articulation of the operated side with the greater trochanter and the shoulder of the implant / rasp visible.

The images will be de-identified and submitted to an assigned medical person for centralized analysis after surgery. The medical person will be assigned by S&N to analyze the fluoroscopic images and to collect the following information on the appropriate CRF:

- distance x_1 between the shoulder of the trial rasp and the tip of the greater trochanter
- distance x_2 between the shoulder of the implant and the tip of the greater trochanter
- diameter of trial head and final ball head

In addition, the following data will be collected during surgery and recorded on the appropriate CRF:

- It will be recorded what type of rasping instrument was used for femoral preparation giving the following options:
 - Slap hammer
 - Woodpecker
 - Mallet
 - Combination
- Information of implanted devices will be recorded on the CRF and by collecting the chart sticks on the CRF.
- The type of the surgical approach will be collected.
- During surgery it will be recorded if the surgeon needed to correct the position of the stem compared to the final rasp and which one of the following methods was used:
 - Smaller ball head length
 - Larger ball head length
 - Removal of stem and enlargement of femoral bed with last trial rasp
 - Other methods

All intraoperative complications will be recorded as outlined in section 8 Safety reporting.

The leg length difference will be measured by the Investigator or designee peri-operatively shortly after surgery before transfer of the subject to the general ward. The length of each lower extremity is determined in cm by measuring the distance between the ASIS and the medial malleolus by using a measuring tape with the subject in supine position. Measured distances will be recorded on the appropriate CRF.

7. SUBJECT COMPLETION AND DISPOSITION

7.1. Screening

Patients considered potential candidates for the study based on the Investigator's initial assessment (pre-screening) must sign an EC approved ICF prior to any study activities. The PI or delegated study research staff will review the eligibility criteria and if determined as eligible will complete the first study assessment (Assessment 1: pre-operative visit) with the subject.

7.2. Enrollment

Subject enrollment occurs at the time of surgery. Every subject that receives the study device will be considered enrolled in the study. If a subject has provided consent and completed screening, and for any reason does not receive study device, the subject will not be considered enrolled in the study.

Therefore pre-operative CRFs will not be submitted to the Sponsor until the subject is actually enrolled (treated with study device) in the study.

7.3. Conditions for Study Termination

Reasons for termination of study participation are described below.

A. Screening Failure

Subjects who have provided informed consent but did not receive the study device are considered screen failures. The reason for screening failure must be captured on the Screening and Enrollment Log maintained in the Investigator Master File. No CRFs will be collected.

B. Voluntary Withdrawal

Study participation is voluntary and subjects may withdraw at any point during the study without giving their reason for doing so. CRFs are collected until time point of withdrawal.

C. Subject Termination by Investigator

The Investigator should withdraw subjects from the study in case the study device cannot be implanted during surgery for any reason.

Subjects that do not receive the study device are not considered as enrolled and will be documented on the Screening and Enrollment Log.

D. Study Termination

The Sponsor may choose to discontinue the study at any time. In which case, the subjects will be followed up according to the standard practice of the site.

E. Study Site Discontinuation

A specific study site in this multicenter study may also warrant termination under the following conditions:

- non-compliance to Good Clinical Practice (GCP) or protocol
- failure to enroll subjects

- inaccurate or incomplete data
- unsafe or unethical practices
- safety or performance considerations

In this case, enrolled subjects will be followed up according to the standard practice of the site.

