#### 6.5. PRIMARY ENDPOINT EVALUATION

Confidential & Proprietary

Once a subject has completed the informed consent procedure and signed the Informed Consent Form (ICF), the Principal Investigator (PI) or delegated study research staff can complete the screening process with the subject. All potential subjects who undergo the screening process will be documented on a Screening and Enrollment Log, on which reasons for exclusion from or denial to participate should be noted. The primary endpoint analysis of the mean difference D between the position of the last trial rasp and the final implant position of the SL-PLUS™ MIA Ti/HA femoral hip stem will be based on full analysis set (FAS) population. The FAS population includes all subjects implanted with a SL-PLUS™ MIA Ti/HA femoral hip stem device in combination with a Smith & Nephew cup with consecutive enrollments to the study. Subjects being a screen failure (CRF plate 99, question 1. Screen Failure Yes) will be excluded from the FAS. A primary endpoint analysis of a sub-group might be performed excluding subjects with low image quality as per defined image review criterias (e.g. trochanter not visible). This depends on the assessment of the independent Image Reviewer.

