## 6.6. SECONDARY ENDPOINTS EVALUATIONS

The secondary endpoint analysis of measurement of leg length discrepancy preoperatively and after insertion of the SL-PLUS™ MIA Ti/HA femoral hip stem (and in addition, collecting intraoperative complications) will also be based on full analysis set (FAS) population.

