## 7.2. STUDY POPULATIONS

All subjects who meet the study inclusion and exclusion criteria will be included in the statistical analysis. **Subjects being a screen failure as documented on “End of Study” – CRF (plate 99) (answer “yes”) will be excluded from the statistical analysis.** Statistical analyses will be conducted for demographics, pre-operative information, surgical information and safety data. Demographics will include, but not limited to, gender, age, weight and height. Pre-operative information and surgical information will include any data collected as defined in this protocol. Safety data will include adverse events, serious adverse event, adverse device effect, serious adverse device effect, unanticipated serious adverse device effect, and device deficiency.

Descriptive statistics for continuous variables will include mean, median, minimum, maximum, standard deviation, and 95% confidence interval, if appropriate. Descriptive statistics for discrete variables will include count and percentage.

Subgroup analyses will be provided if they are necessary. The following sections define the details of primary endpoint and secondary endpoints analyses.

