## 12.9. END OF STUDY

**Table 47: Screen Failure**

Screen Failure	Total N = xx (%)
No	
Yes	Excluded from analysis.
If yes, reason	

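### A complication that prevents implantation of the stem cannot enter the intraoperative-complication summary, which covers implanted subjects only

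*Protocol*

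**What the plan says.** Protocol 2.2 lists the secondary endpoints and adds: "In addition, intraoperative complications will be collected". Protocol 6.1.2 says that all such complications are to be recorded, through the safety section.

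For a consented subject who does not get the stem, Protocol 7.2 rules that one who "for any reason does not receive study device, the subject will not be considered enrolled in the study". Protocol 7.3, item C, applies this to subjects already in theatre: "The Investigator should withdraw subjects from the study in case the study device cannot be implanted during surgery for any reason". Item A of the same section classes every consented non-recipient as a screen failure, asks for the reason on the site's Screening and Enrollment Log, and adds: "No CRFs will be collected".

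SAP 6.5 defines the FAS as subjects implanted with the study stem (with a cup from the sponsor) and states: "Subjects being a screen failure (CRF plate 99, question 1. Screen Failure Yes) will be excluded from the FAS". SAP 6.6 says the secondary endpoint analysis, complications included, "will also be based on full analysis set (FAS) population". SAP 7.2 says that screen failures "will be excluded from the statistical analysis", and Table 47 marks them "Excluded from analysis".

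**The concern.** Entry to the complication summary depends on the stem having been implanted, and a complication is one thing that can prevent implantation. Inclusion therefore depends on an event that the outcome itself can cause. A complication bad enough to make the surgeon abandon the study stem is one a reader of this table would want to see, and it is the one kind the table cannot show. At stake is how complete a descriptive safety table is. The primary endpoint is not touched: without an implanted stem there is no second distance to measure.

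**Working it through.** **Step 1: follow one case through the rules.** Take a consented, eligible subject in whom a complication occurs in theatre and the study stem is not implanted.

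- Protocol 7.3 C: withdrawn by the investigator.
- Protocol 7.2: not enrolled.
- Protocol 7.3 A: screen failure, reason on the log, no CRFs. (Item B, by contrast, keeps the CRFs of a voluntary withdrawal up to the time of withdrawal.)
- SAP 6.5: outside the FAS, both because not implanted and because a screen failure.
- SAP 6.6: complications are analysed on the FAS, so the case is not counted.
- SAP 7.2 and Table 47: excluded from the rest of the analysis as well.

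The case adds 0 to the numerator and 0 to the denominator.

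**Step 2: look for another route into the summary.**

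- The log and the reason row of Table 47 can hold a reason. Neither is a complication record, and Table 47 does not separate operated subjects from those never operated on.
- The disposition counts (SAP 8.1, Table 3) show attrition, not its cause.
- Protocol 8.2 and 8.3 give the investigator recording and reporting duties, so the sponsor may hear of the event. Whether they reach a subject who was never implanted is unclear, because section 8 counts from implantation of the device. They also run through a CRF that 7.3 A does not collect.

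None of these feeds the complication summary.

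**Step 3: size.** The documents state no figure for this endpoint, so there is none to reproduce. They give neither a rate of abandoned implantation nor the share due to a complication. All counts below are assumed, except the planned 40 implanted subjects (Protocol 3, SAP 6.1).

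Let a = implanted subjects with a complication, c = operated, non-implanted subjects with one, and o = other operated, non-implanted subjects.

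- Rate as planned: a/40
- Rate among all operated: (a + c)/(40 + c + o)

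With exact (Clopper-Pearson) 95% intervals:

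| a | c | o | As planned | All operated |
|---|---|---|---|---|
| 0 | 1 | 0 | 0/40 = 0% (0 to 8.8%) | 1/41 = 2.4% (0.06 to 12.9%) |
| 0 | 2 | 0 | 0/40 = 0% (0 to 8.8%) | 2/42 = 4.8% (0.6 to 16.2%) |
| 2 | 0 | 2 | 2/40 = 5.0% (0.6 to 16.9%) | 2/42 = 4.8% (0.6 to 16.2%) |
| 2 | 1 | 1 | 2/40 = 5.0% (0.6 to 16.9%) | 3/42 = 7.1% (1.5 to 19.5%) |
| 2 | 2 | 0 | 2/40 = 5.0% (0.6 to 16.9%) | 4/42 = 9.5% (2.7 to 22.6%) |

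**Step 4: direction.** (a + c)/(40 + c + o) > a/40 holds exactly when 40c > a(c + o), that is, when c/(c + o) > a/40. With a = 2 the break-even is 2/40 = 5%. The planned rate is the lower one only if complications are more frequent among the non-implanted than among the implanted. The third row goes the other way.

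**Step 5: how likely is one such case?** Let p be the share of operations in which implantation is abandoned and q the share of those due to a complication. The chance of at least one complication-caused abandonment before 40 stems are implanted is 1 − [(1 − p)/(1 − p + pq)]^40. For example, p = 1% and q = 0.5 give 1 − (0.99/0.995)^40 = 18.3%.

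| p (assumed) | q = 0.25 | q = 0.5 |
|---|---|---|
| 0.5% | 4.9% | 9.6% |
| 1% | 9.6% | 18.3% |
| 2.5% | 22.6% | 39.9% |

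**The case against.** The strongest reply is that this is a disclosed design choice. The study is a post-market, single-arm case series about rasp and stem position. Protocol 3 and SAP 6.1 describe 40 implanted subjects, and SAP 6.5 and 6.6 together say that complications are analysed in implanted subjects. A reader might infer that the plan conditions on implantation without saying so. It does not: the SAP's FAS definition states the restriction, and no document promises an all-operated safety set. That part of the reply stands. What it does not answer is that Protocol 6.1.2 undertakes to record all intraoperative complications, while 7.3 removes the forms for one class of them.

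The reply can add that Table 47, the disposition table and the log already give counts and reasons. This stands in part: what is missing is the split between operated and never-operated screen failures, and their place beside the complication rate.

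Three further inferences should be resisted.

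- *Safety oversight is lost.* This is not shown. Nothing in Protocol 8.2 or 8.3 limits the investigator's duties to enrolled subjects, although section 8 leaves their reach unclear.
- *Complications during rasping are lost in subjects who are later implanted.* Section 8 counts from implantation, but Protocol Table 1 schedules adverse event assessment at surgery and 6.1.2 covers all intraoperative complications. No loss is shown.
- *The summary bears directly on improving the instruments.* Protocol 10.4 speaks of the study's information in general and does not tie that use to the complication table.

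**Conclusion.** The point holds as a cheap improvement. The text is clear on the main matter: a stated rule, not an omission, keeps complications that prevent implantation out of the summary.

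The size is modest and wholly assumed. Protocol 9.2.2 makes the endpoint descriptive, and SAP 7.3 seeks no claims from secondary measures. At the lower assumed rates, the chance of even one such case is about 5 to 10%. If one occurs, the report could show 0% where the all-operated figure is 2.4%, with widely overlapping intervals. A reader might infer that the planned rate must be too low. The documents do not support that, because the direction depends on how often complications occur among non-implanted subjects, which they do not give. The primary analysis, sample size and power do not change.

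**What to change.** 1. **Data collection.** Amend Protocol 7.2 and 7.3 so that operative, adverse event and device-deficiency CRFs are collected for consented subjects whose surgery for the study stem was started but who were not implanted. Keep screen-failure status without these forms for subjects whose surgery was never started.
2. **Analysis set.** Amend SAP 6.5, 6.6, 7.2 and Table 47 to add a safety set of all consented subjects whose surgery for the study stem was started. Base the complication, AE, SAE and device-deficiency summaries on it, showing implanted and non-implanted subjects separately. Leave the primary-endpoint set as it is.
3. **Minimum alternative.** If the implanted-only set is kept, label the complication rate as being among implanted subjects. List beside it the operated, non-implanted subjects with reasons, apart from screen failures never operated on.
4. **Wording to reconcile in any case.** Protocol 7.3 collects no CRFs for screen failures, while SAP 6.5 and 7.2 identify them from the End of Study CRF (plate 99). Either reading leaves the subject out of the analysis, but the two texts should agree.

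The cost is wording in these sections, a few extra forms and one more analysis set.
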